Timeline (weeks)*		0		2	4	8-52	9-53	12-56	20-64	32-76
Time windows (days)	-90 to -7		+1	+3	+5	+5	+1	+5	+5	+14
Vaccination, ChAdOx1 85A or BCG		x								
Vaccination, MVA85A [§]						x [§]				
Inclusion/exclusion criteria	x	x								
Review contra- indications	x	x				x				
Informed consent	x									
Medical history	x	(x)	(x)	(x)	(x)	(x)	(x)	(x)	(x)	(x)
Physical examination	x	(x)	(x)	(x)	(x)	(x)	(x)	(x)	(x)	(x)
Vital signs	x	x	x	x	x	x	x	x	x	x
Urinalysis	x									
β-HCG urine test (female only)	x	x				x				
Stool parasitology	x	x	x							x
Anthelminthic treatment									x	
Local & systemic events/reactions		x	x	x	x	x	x	x	x	x
Diary cards provided		x				x				
Diary cards collected				x			x			
Biochemistry (4mL)**/***	x			x		x	x			
HBV, HCV, HIV (6mL)	x									
Haematology: full blood count and storage (2mL)	x		x	x		x	x		x	x
Mansonella perstans (1mL)***	x									x
Malaria RDT/slide; PCR (1mL)	x	x***		x	x	x		x		x
Assessments of immunogenicity and exploratory immunology incl ELISpot (10-20mL)****	x	x	x	x	x	x	x	x	x	x
Gene expression (2mL)	x		x							
Blood vol (mL)	26	10	16	28	5	13	28	5	5	24
Cumulative blood vol (mL)	26	36	52	80	85	98	126	131	136	160

X Event scheduled to occur

(X) If considered necessary, emphasising any complaint or change in medications

* Timeline is approximate only, as exact timings (\pm windows periods) of visits relate to the actual (not intended) date of the previous visit

§ Group 5 only

** Urea & electrolytes, liver function tests

*** Repeated on vaccination day if delay from screening is more than 28 days

**** Exploratory immunology blood volume will be guided by guidelines from Harvard Mass General, where a maximum of 3ml/kg body weight is taken at any one time point and not more than 3ml/kg is taken over any 8 week period (ref http://www.drgreene.com/21_1616.html.) These guidelines have been followed in previous

studies vaccinating adolescents and children with MVA85A (in South Africa [1]). The total blood volume planned is 98 ml over the initial intensive sampling period of 8 weeks. Revision of sample volumes based on weight will only be required for children who weigh less than 33 kg; the average weight of children aged 11 is expected to be greater than 35kg, with greater weights for older children.

a Participants will have variable follow up days depending on whether they were enrolled before or after the COVID 19 lockdown

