6. OBJECTIVES AND OUTCOME MEASURES

Objectives	Outcome Measures	Timepoint(s) of evaluation of this outcome measure
Primary Objective To evaluate the safety and immunogenicity of ChAdOx1 85A – MVA85A prime-boost vaccination in Ugandan adolescents	Actively and passively collected data on adverse events	All Adverse Events (AEs) from day 0-28 post vaccination Serious Adverse Events (SAEs) throughout follow up
	T-cell Interferon- γ ELIspot response to antigen 85A	ELIspot spot-forming counts per 1×10^6 peripheral blood mononuclear cells (PBMCs) at day 14 for groups 1-4 ELIspot spot-forming counts per 1×10^6 peripheral blood mononuclear cells (PBMCs) at day 63 for groups 5 and 6 Area under the curve (AUC) analysis of immunogenicity (days 0-168 for groups 1-4; days 0-168 for groups 5 and 6)
Secondary Objective To further characterise immunogenicity of ChAdOx1 85A – MVA85A prime-boost vaccination in Ugandan adolescents	Antibody response to antigen 85A Exploratory immunology including ELIspot response to BCG, flow cytometry, gene expression, and mycobacterial killing assays	Screening and follow up visits as shown in Schedule of Visits, section 3
Tertiary Objectives 
 
To compare the response to ChAdOx1 85A – MVA85A prime-boost vaccination with the response to BCG revaccination in Ugandan adolescents 
To compare the response to ChAdOx1 85A – MVA85A prime-boost vaccination in Ugandan adolescents with the response in Oxford adults 
To investigate pre-immunisation epidemiological and immunological characteristics associated with the immune response induced by ChAdOx1 85A – MVA85A prime-boost vaccination in Ugandan adolescents 	T-cell Interferon- γ ELIspot response to antigen 85A Antibody response to antigen 85A, exploratory immunology including T cell ELIspots, flow cytometry, gene expression, and mycobacterial killing assays	Primary outcomes for these analyses will be antigen 85A specific ELIspot spot-forming counts per 1×10^6 peripheral blood mononuclear cells (PBMCs) at day 63 from the first vaccination and ELIspot AUC analysis Additional outcomes using data from follow up visits as shown in Schedule of Visits, section 3 Screening and follow up visits as shown in Schedule of Visits, section 3

Table 4. Objectives and Outcome Measures

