The follow up period for those enrolled after the COVID 19 lockdown will be 24 weeks after first vaccination and 24 weeks after booster vaccination for those enrolled before the lockdown in accordance with findings from previous studies in which adequate safety data and reliable markers of immunogenicity have been obtained in this time interval. Due to the nearly three months COVID-19 lockdown and halting of trial activities, participants who had already been enrolled in the trial by that time will have a later MVA85A vaccination boost ranging up to **52** weeks (instead of 8 weeks) after initial vaccination with ChAdOx1 85A. Their subsequent follow up visits will be at day 7, day 28, 3 months and 6 months post boost vaccination. Their follow up visits will therefore fall within the following ranges of **63-372**, **84-393**, **140-449** and **224-533** days. Newly enrolled participants into Group 5 will follow the original schedule of the MVA85A boost at day 56 and subsequent follow up visits on days 63, 84, 140 and 224. All follow up visits will last approximately 15 to 30 minutes. Most of the participants are currently in secondary school which are either day or boarding. For logistical and time management purposes as well as to minimize disruption of their studies, participants in boarding schools will be offered the option of having follow up visits done at the school premises. A qualified clinician and nurse will visit the school with the necessary supplies and equipment for the visit on the said date. The clinician will examine and assess the participant while the nurse will draw blood and collect the relevant samples for that visit. The trial team will seek permission and a formal introductory letter from the district education officials to the school management for access to the schools. The team will secure suitable space for these activities. The team will ensure the participant

is in a good health condition before departing from the school. The study contact phone number will be availed to the school to follow up on any concerns.

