11. STATISTICS

This is primarily an exploratory immunogenicity and safety trial with descriptive endpoints.

Adverse events will be listed and summarised by type of AE, frequency, severity and trial group.

The sample size (12 participants for dose escalation and age de-escalation, 60 participants [30 in each arm] for the randomised trial) has been determined by the number of doses of ChAdOx1 85A available for this study. The following are the considerations regarding sample size for the randomised component of the trial. The primary outcome is the IFN- γ ELIspot response to antigen 85A at week 9 which is measured in spot forming counts per 1×10^6 peripheral blood mononuclear cells (PBMCs). Assuming a standard deviation of $0.4 \log_{10}$ sfc/ 1×10^6 PBMC (spot forming counts/ 1×10^6 peripheral blood mononuclear cells) in the peak Ag85A response, our study will have over 80% power to detect a difference of $0.29 \log_{10}$ in sfc/ 10^6 PBMC with $p < 0.05$. This is comparable to the difference that was observed between the response to human adenovirus vectored TB vaccine candidate Aeras 402 alone (Day 14 post Aeras) and Aeras 402 with MVA85A boost (Day 7 post MVA boost) [21], or between BCG (Day 28) and MVA85A alone (Day 7) in UK subjects [62], and hence a reasonable difference to expect between BCG and ChAdOx1 85A-MVA85A (aim 2).

For outcomes that are approximately normally distributed or normalised by log-transformation, differences in means will be presented together with 95% confidence intervals and p-values from unpaired t-tests. For non-normally distributed outcomes, the difference in medians between the two groups will be presented along with its 95% confidence intervals, and p-values from Wilcoxon ranksum tests.

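### The comparison of groups 5 and 6 on post-boost Ag85A ELISpot makes no use of a pre-vaccination Ag85A value, so a trial sized by vaccine doses may give up some precision

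*Combined protocol and SAP*

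**What the plan says.** **Analysis.** Section 11 calls the trial primarily exploratory with descriptive endpoints. It names the Ag85A ELISpot at week 9 as the outcome of the randomised part. For outcomes that are normal, or normal after a log transform, "differences in means will be presented together with 95% confidence intervals and p-values from unpaired t-tests". For other outcomes it gives a difference in medians and a rank-sum p-value. It names no covariate and no change from baseline.

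**Role of the comparison.** Table 4 in Section 6 places the outcome at "peripheral blood mononuclear cells (PBMCs) at day 63 for groups 5 and 6". It lists the comparison of ChAdOx1 85A – MVA85A "prime-boost vaccination with the response to BCG revaccination in Ugandan adolescents" as tertiary. That is nevertheless the comparison whose power Section 11 works out. Section 11 also says that available ChAdOx1 85A doses determined the sample size.

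**Baseline sampling.** Table 4 includes "Area under the curve (AUC) analysis of immunogenicity (days 0-168 for groups 1-4; days 0-168 for groups 5 and 6"). The row "Assessments of immunogenicity and exploratory immunology incl ELISpot (10-20mL") is marked at screening, at day 0 and at every later visit. In groups 5 and 6 (Section 3.3), 10 mL is drawn at day 0. The only other blood test marked there is malaria, which carries the footnote "Repeated on vaccination day if delay from screening is more than 28 days".

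**What is not said.** No section states which pre-vaccination sample is tested for Ag85A. The only antigens named for the screening ELISpot are ESAT6 and CFP10 (Section 7.5).

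**The concern.** In a randomised comparison, a pre-vaccination measurement of the outcome variable can absorb between-person variation that otherwise stays in the error term. There is reason to expect such variation here. Section 5.1.2 says that all mycobacterial species sequenced to date express antigen 85A, and Section 7.4 requires BCG near birth in all adolescents. Tertiary objective 3 asks whether pre-immunisation immunological characteristics are associated with the response, so the sponsor treats this as an open question.

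What is at stake is the width of the interval for the one comparison that Section 11 powers. The planned size gives almost exactly 80% power, and more participants would need more doses. A covariate that the plan seems likely to collect anyway is one of the few remaining ways to gain precision.

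**Working it through.** **Inputs from Section 11:** SD 0.4 log10, difference 0.29 log10, 30 per arm, p < 0.05 (taken as two-sided, which reproduces the stated figure).

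**1. The plan's own figure.**
- SE = 0.4 × √(2/30) = 0.1033, and 0.29 / 0.1033 = 2.808.
- Normal formula: power = Φ(2.808 − 1.960) = Φ(0.848) = 80.2%.
- Exact noncentral t, 58 df: 78.8%.
- 95% CI half-width = 2.0017 × 0.1033 = 0.207 log10, a factor of 10^0.207 = 1.61 on the geometric mean ratio.

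The stated figure of over 80% is reproduced by the normal formula.

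**2. ANCOVA on a baseline with within-arm correlation r.** The residual SD is 0.4 × √(1 − r²). Estimating the slope multiplies the variance by 1 + 1/(60 − 4) = 1.0179, a factor of 1.0089 on the SE. So SE = 0.1033 × √(1 − r²) × 1.0089, with 57 df and critical value 2.0025. Every r is an assumption.

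| r | SE | Power | CI half-width (log10) | t-test n per arm for the same power |
|---|---|---|---|---|
| planned t-test | 0.1033 | 78.8% | 0.207 | 30 |
| 0 | 0.1042 | 78.1% | 0.209 | – |
| 0.1 | 0.1037 | 78.5% | 0.208 | – |
| 0.2 | 0.1021 | 79.7% | 0.204 | 31 |
| 0.3 | 0.0994 | 81.8% | 0.199 | 33 |
| 0.5 | 0.0902 | 88.5% | 0.181 | 39 |

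Break-even is r = 0.135. At r = 0 the cost is 78.8 − 78.1 = 0.7 points.

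**3. What shrinks the gain** (simulated power, ANCOVA v t-test, 30 per arm; all scenario inputs assumed).
- *Unequal r by arm:* 0.5 and 0.1 give 81.8 v 78.9%; 0.3 and 0.1 give 79.9 v 78.9%.
- *Low baseline counts* (geometric mean 10 sfc, background 5 sfc): an underlying r of 0.5 is observed as 0.39, giving 84.1 v 78.6%; 0.3 is observed as 0.23, giving 80.3 v 79.0%.
- *Delayed boosts:* Section 7.9 ties later visits to the boost ("Their subsequent follow up visits will be at day 7, day 28, 3 months and 6 months post boost vaccination"), and the boost may come up to 52 weeks after the prime, so the baseline may be a weaker predictor. With half delayed, and r falling from 0.5 to 0.25 in them, 84.0 v 79.1%; from 0.3 to 0.15, 80.2 v 79.0%; from 0.3 to 0, 79.0 v 78.8%. With three quarters delayed and r falling from 0.3 to 0, ANCOVA loses: 78.2 v 78.7%.

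Type I error was 4.8–5.2% for both tests with normal data and with low counts. It was not checked in the delayed-boost set.

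**4. Missing baselines.** If a share m is filled with the overall mean, the squared correlation becomes (1 − m)r². With half missing, r = 0.5 becomes 0.5 × √0.5 = 0.354 (power 83.3%), and r = 0.3 becomes 0.212 (about 80%).

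**The case against.** **No defect is shown.** An unadjusted test is valid under randomisation and is a legitimate, simple choice for a trial with descriptive endpoints. This stands. A reader might infer that the t-test is biased or that the power statement is wrong. The documents support neither: the power reproduces, and adjustment changes only the variance.

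**The benefit rests on an unknown r.** This stands too. Neither r nor any baseline Ag85A level is given. Excluding people with ESAT6 or CFP10 responses could narrow the baseline spread. In the complicated scenarios that start from r = 0.3 in both arms, the gain is at most 1.3 points and once becomes a small loss.

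**A day-0 Ag85A assay is not established.** A reader might infer one from the AUC, which starts at day 0. That does not follow. Groups 1–4 have the same days 0–168 AUC and the same marked row, yet Section 3.2 shows 0 mL drawn at day 0. Their starting value may therefore come from screening. The 10 mL day-0 draw in groups 5 and 6 supports an immunology sample, but it does not identify the assay or antigen. The row's 10–20 mL label is also an unreliable guide, since days 28, 84 and 140 carry the same mark with 5 mL of blood in total. What survives is narrower: the AUC needs some starting value, and one of the two pre-vaccination samples would have to supply it.

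**Conclusion.** The point holds as an optional efficiency improvement. The planned analysis leaves out a pre-vaccination Ag85A value that the plan implies but does not locate. Adjusting for it would change power by about −0.7 points at r = 0, +3 at r = 0.3 and +10 at r = 0.5. The CI half-width would fall from 0.207 to 0.199 or 0.181 log10 at the last two values.

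This rests on the Section 11 SD and difference, on a common r within arms, and on a baseline assay that exists for most participants. Low counts, delayed boosts and missing baselines each reduce the gain. The documents do not support saying that baseline Ag85A predicts the response, only that it may.

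Two neighbouring matters are separate and add no weight here: week 9 against the visit range of days 63–372, and the choice of estimate to accompany the rank-sum test.

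**What to change.** In a dated amendment or SAP, made before outcome data by arm are seen:
- State which pre-vaccination sample is tested for Ag85A in groups 5 and 6.
- Make the main between-arm analysis an ANCOVA of log10 Ag85A ELISpot at the planned post-boost visit, on arm and log10 pre-vaccination Ag85A ELISpot (day 0 where assayed, otherwise screening).
- Fix the zero-count offset in advance, for example 1 sfc per 10^6 PBMC.
- Impute a missing baseline without regard to arm, for example with the overall mean, so that nobody is dropped.
- Report a geometric mean ratio with its 95% CI.
- Keep the unadjusted t-test and the rank-sum test as sensitivity analyses.

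**Cost.** No extra doses or visits, and about 0.7 points of power if r is near 0. The date matters because the trial is open label (Section 7.8) and enrolment began before the lockdown (Section 7.9). For participants already enrolled, a day-0 assay cannot simply be declared. If neither pre-vaccination sample was tested for Ag85A, the value could come only from stored cells, where Section 7.10 consent and supply allow; otherwise it is imputed and the gain falls as shown.

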8.4.1. Subsequent visits

All volunteers will be asked to attend as per the Schedule of Visits and Procedures in section 3. On visits other than for vaccination the volunteers will be assessed for local and systemic adverse events, using paper diary cards, interim history, physical examination and blood tests at the time-points indicated in the Schedule of Visits and Procedures (Section 3). Blood will also be taken for assessments of immunogenicity and exploratory immunology analysis. These follow up visits may be done at school (see section 7.9).

8.4.2. MVA85A booster immunisation.

Volunteers in group 5 will be asked to attend between day 56 and day **365** for booster immunisation with MVA85A [volunteers in group 6 will also be asked to attend on this date, but only to provide the samples indicated]. For participants who were enrolled in the trial prior to the COVID-19 lockdown, this boost visit will fall between day 56 and day **365** after enrolment into the trial while for newly enrolled participants, the boost will be done on day 56.

For group 5, before the MVA85A vaccination, the health of the volunteer will be reviewed. Pulse, blood pressure and temperature will be observed and if necessary, a medical history and physical examination may be undertaken to determine need to postpone booster vaccination. For girls, a pregnancy test will be repeated. If the volunteer is well and the pregnancy test is negative MVA vaccination will be administered at 1×10^8 pfu.

Group 5 volunteers will be provided with a diary card and instructed in its use as described above.

Diary cards will be collected two weeks after ChAdOx1 85A and one week after MVA85A as these intervals correspond to the optimal time points for assessing the initial response to the two vaccines.

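### The planned between-arm test has no term for enrolment before or after the lockdown, although the two cohorts are sampled on different timetables; if responses differ by cohort, precision is lost

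*Combined protocol and SAP*

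**What the plan says.** Section 11 gives the whole comparative analysis in two sentences. For outcomes that are normal, or normal after log-transformation, "differences in means will be presented together with 95% confidence intervals and p-values from unpaired t-tests"; for the rest, a difference in medians with a Wilcoxon rank-sum p-value. Neither has a covariate or stratum. The size is "60 participants [30 in each arm] for the randomised trial", a number that "has been determined by the number of doses of ChAdOx1 85A available for this study". The outcome used for the power statement is fixed in time: "The primary outcome is the IFN- γ ELIspot response to antigen 85A at week 9" (day 63 in Table 4).

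The visit timetable is no longer fixed. Section 7.9 says that "participants who had already been enrolled in the trial by that time will have a later MVA85A vaccination boost", up to 52 weeks after the prime, which puts their 7-day post-boost visit anywhere from day 63 to day 372. Newly enrolled group 5 participants keep the boost at day 56 and visits on days 63, 84, 140 and 224. Group 6 moves too: under the booster heading (8.4.2), "volunteers in group 6 will also be asked to attend on this date", for samples only, and footnote a of Table 1.2 applies the variable days to both groups.

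Section 7.8 describes no stratification by cohort and no block size. The only adjustment mentioned anywhere is for location of residence (Section 7.2). The amendment history for versions 4.0 and 4.1 lists changes to 3.3, 7.9 and 8.4.2, and none to Section 11.

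**The concern.** The amendments turned the randomised part into two cohorts. Cohort is fixed by the calendar date of enrolment, cannot be affected by the arm, and is tied to the prime-boost interval in group 5 and to the time since BCG in group 6 when the main ELISpot sample is taken. That is a natural variable to prespecify, and the planned test does not use it.

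Two things are at stake. If responses differ between cohorts, the difference goes into the residual variance and power falls; the number of participants is capped by vaccine supply, so precision cannot be bought back with a larger sample. And a single pooled difference does not show whether the effect at the intended interval resembles the effect after a long delay. A cohort term added after the data are seen would look post hoc.

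**Working it through.** **Inputs from Section 11:** 30 per arm; difference 0.29 log10; SD 0.4 log10; p < 0.05, taken as two-sided because sidedness is not stated.

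**The plan's own figure.** The standard error of the difference is 0.4 × √(2/30) = 0.1033, and 0.29/0.1033 = 2.808. By normal approximation, power = Φ(2.808 − 1.960) = 80.2%, which reproduces the claim of over 80%. With the noncentral t on 58 df it is 78.8%. That small gap is not the point here; the t-based figure is the baseline below.

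**Assumptions not in the documents:** the pre-lockdown share p, the cohort shift c in log10, and that 0.4 is the SD within a cohort. Each is shown as a range.

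**Shift common to both arms, no cohort term.** Total SD = √(0.4² + p(1 − p)c²). For example, p = 0.5 and c = 0.4 gives √(0.16 + 0.04) = 0.447. Power is noncentral t, 58 df:

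| p | c = 0.2: SD, power | c = 0.4: SD, power | c = 0.6: SD, power |
|---|---|---|---|
| 0.10 | 0.405, 78.0% | 0.418, 75.3% | 0.439, 71.2% |
| 0.25 | 0.409, 77.0% | 0.436, 71.7% | 0.477, 63.9% |
| 0.50 | 0.412, 76.4% | 0.447, 69.5% | 0.500, 59.8% |

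With c = 0 the power is 78.8% and nothing is lost. A cohort main effect removes p(1 − p)c² and returns power to 78.8% (57 df); when the arms are balanced on cohort, the lost degree of freedom costs about 0.02 points.

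**When the shift is not common.** Simulated power, 6,000 runs per row (Monte Carlo standard error about 0.5 points), p = 0.5, cohorts balanced across arms, average effect 0.29:

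| Cohort shift | t-test | + cohort | + cohort and interaction |
|---|---|---|---|
| none | 79.8% | 79.9% | 79.7% |
| 0.4 in both arms | 71.4% | 79.0% | 79.0% |
| 0.4 in one arm only | 74.3% | 76.3% | 78.2% |
| 0.2 in opposite directions | 75.7% | 75.5% | 77.7% |

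The normal approximation agrees for the one-arm case: 80.2% without a shift, 75.4% for the t-test (SD √0.18), 77.8% with the main effect (SD √0.17). About half of the loss is recovered. For opposite shifts the main effect recovers nothing.

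**Precision of the descriptive results.** The half-width of a within-cohort 95% CI is t × 0.4 × √(2/m), with m per arm in that cohort: m = 15 gives 2.048 × 0.146 = 0.30; m = 9 gives 2.120 × 0.189 = 0.40. For the interaction (56 df) it is 2.003 × 0.4 × √(2/15 + 2/15) = 0.41 at 15:15 and 2.003 × 0.4 × √(2/9 + 2/21) = 0.45 at 9:21.

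**The case against.** The strongest reply is that nothing in the plan is invalid. Under randomisation the unpaired comparison is unbiased, and chance imbalance of cohort is ordinary sampling error that the confidence interval covers; the total-SD figures already include it, so it is not a second loss. That stands. A reader might infer a biased or invalid test, and the documents do not support that.

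Second, the loss is conditional. A reader might take it as established that the plan loses power, but the documents report no cohort difference in ELISpot, no number enrolled before the lockdown and no split by arm. The large losses need shifts of 0.4 to 0.6 log10, which is 1.0 to 1.5 of the assumed SD. That stands too.

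Third, a reader might infer that a stratum term would recover whatever is lost. Delayed group 5 participants are still sampled 7 days after boost, and what changes is the prime-boost interval; in group 6 it is the time since BCG. Nothing suggests that these produce equal shifts, and for unequal shifts a main effect recovers part or none. This is why the model needs the interaction.

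Fourth, cohort does not determine timing. The early range, day 56 to day 365, includes the schedule of the later cohort, so a two-level term leaves variation in delay within the early cohort in the error.

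Finally, Section 11 calls the trial exploratory with descriptive endpoints, and Table 4 lists the BCG comparison as tertiary. That lowers the stakes, but Section 11 still commits to p-values, confidence intervals and a power claim for this comparison, and none of these replies makes the cohort term harmful.

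**Conclusion.** The point holds as one of precision and prespecification. Section 11 ignores a variable that is fixed at enrolment, already on record and tied to sampling time in both arms. With a shift common to both arms and a pre-lockdown share of 10% to 50%, t-based power for 0.29 log10 goes from 79% to about 76-78% for a shift of 0.2 and 70-75% for 0.4; with no shift it is unchanged. Share, shift and the reading of 0.4 as the within-cohort SD are assumptions. Full recovery by a main effect also requires the shift to be the same in both arms.

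A cohort term does not settle which visit stands for week 9 or day 63 when the 7-day post-boost visit can fall as late as day 372. Sections 6, 7.9 and 11 must be reconciled on that first. Section 8.4.3 also still gives day 140 as the latest boost day, where 7.9 and 8.4.2 give 52 weeks or day 365; those passages must be reconciled as well. The cohort point stands under either limit.

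**What to change.** In Section 11, replace the unadjusted comparison with a linear model on log10 ELISpot, and on the AUC, containing arm, enrolment cohort (before or after the lockdown, centred at its mean) and their interaction. Take the arm effect averaged over cohorts as the result, with its 95% CI and p-value. In the non-normal branch, use a van Elteren rank test stratified by cohort in place of the Wilcoxon test.

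Report the arm difference within each cohort with 95% CIs, and the interaction, as descriptive only. State in advance that these will be imprecise: about ±0.3 log10 or wider in the smaller cohort, which already exceeds the 0.29 target, and about ±0.41 to ±0.45 for the interaction in the splits shown. Note also that the two-level term does not capture variation in delay within the early cohort.

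The cost is a few lines in Section 11 and one degree of freedom for cohort, or two with the interaction. No new data are needed. State in the same revision which visit is analysed as week 9 for delayed participants; that is a separate change.
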